The primary outcome variable is the orbital volume of the injured orbit compared to the contralateral uninjured orbit as assessed by CT scan with OsiriX medical imaging software (OsiriX MD 8.5.2) **at immediate post-operative hour**.

Accordingly, the primary outcome variable will be classified as:

- A. The absolute reduction in orbital volume from the measured post-traumatic volume, as measured by CT.

The secondary outcome variables will be recorded 1 week, 3 weeks, and 6 weeks postoperatively.

The secondary outcome variables include the following:

- 1- Adequate orbital volume reduction, defined as a reduction of orbital volume to **less than 2 cm³**.
- 2- Unsatisfactory orbital volume, defined as a final orbital volume **more than 2 cm³**
- 3- Post-operative variables: enophthalmos, infection, infraorbital nerve injury, traumatic pupillary mydriasis, orbital compartment syndrome, extra-ocular motility, and plate contour.
- 4- Operating time.
- 5- Length of stay (LOS).
- 6- Treatment charges.

The following are details regarding secondary outcome variables:

- Enophthalmos as assessed by clinical examination using a Hertel exophthalmometer.
 - A difference of more than 2 mm between the two orbits is diagnostic for enophthalmos.⁽⁴⁾
- Infection
 - As defined by the presence of post-operative pus in the wound, a sinus tract or fistula, or elevated WBC >11.0x10⁹/L combined with erythematous skin and swelling on the operated side more than on the un-operated side.
- Infraorbital nerve injury as assessed by clinical examination using neurosensory testing (NST).
 - i. NST is a standardized methodology designed to objectively evaluate sensory nerve function.⁽²²⁾ The sensory impairment is determined by 3 levels of testing; each level classifies a specific type of sensory nerve injury.^(22, 23)
 - ii. All patients will be assessed for the development of altered sensation of the infra-orbital nerve that:
 - A. Did not present prior to the surgery.
 - B. Did not improve after the surgery.
- Traumatic pupillary mydriases as assessed by pupillary size measurement in millimeters.
 - All patients will be assessed for the development of post-operative traumatic pupillary mydriasis that did not present prior to the surgery.
- Orbital compartment syndrome as assessed through clinical examination using tonometers.
 - Intra-ocular pressure (IOP) > 40 mmHg is diagnostic of orbital compartment syndrome.

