We expect a **sample size of 60** surgical cases, evenly split between the new treatment and control groups, to have a study powered to **detect at least a 1 cm³ difference in orbital volume** between the groups. The sample size calculation was based on using a two-sample Student's t-test to compare the difference in contralateral orbital volume between the treatment and control groups. We used a **power of 90%**, alpha level of .05, and 1.17 cm³ standard deviation of orbital volume. The 'normal' orbital volume and standard deviation were estimated from the results of Forbes et al. (1984). Sample size calculations were performed with the 'power.t.test' function in R statistical software based on Cohen (1988).⁽²⁵⁾ Taking attrition into account, if 25% of our expected patient enrollment numbers are not met for any reason, **our study would still retain a power of 80%**. Additionally, in the event of attrition from loss-to-follow-up alone, our primary outcomes variable and the bulk of the secondary outcomes variables, including the reduction of orbital volume to less than 2 cm³, operative time, traumatic pupillary mydriasis, orbital compartment syndrome, extra-ocular motility, and plate contour, will be successfully obtained on immediate post-operative hour. **Attrition at these stages will have no effect on the above variables.**

Randomization & Statistical Analysis

Cases will be randomized to the treatment or control arms using a pre-generated block randomization scheme with a **block size of 4** and stratified according to surgeon/specialty. In essence, each surgeon will receive their own list of randomized cases to simplify the logistics of the trial. **The block randomization guarantees that at no point during the trial will there be more than a 3-case difference between the treatment and control arms for each individual surgeon**; thus, it is possible but unlikely that there will be a maximum 9 case difference at some

point (sizes will be equal at completion). The randomization scheme has been pre-generated by a statistician, and the resulting trial arm for each case will be placed in envelopes to be revealed at the time of patient enrollment. The treatment will not be blinded to the physician or the patient; it is not practical to keep knowledge of the procedure concealed.

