The success of the randomization will be evaluated at the start of the analysis by comparing patient characteristics. Differences between the treatment and control arms that do not reach statistical significance using appropriate tests (likely t-tests and chi-square tests) that are smaller than 20% for all characteristics will mean that the groups are ‘balanced’ in our criteria and will be evidence of randomization success. Assuming that standardization is successful, all outcomes will be compared using standard two-sample comparisons. For binary outcomes, such as complications and CT use, Chi-square tests or Fisher’s exact tests will be used depending on the prevalence of the outcome. Two-sample t-tests or Wilcoxon-Mann-Whitney tests (if data are non-parametric) will be used to compare mean orbital volume differences and operative times. Differences in length of stay and costs are likely to be analyzed with two sample t-tests on a log scale (thus, a comparison of geometric means will be made). Finally, logistic regression or other multivariable analyses may be performed to identify risk factors for developing complications or deviations from the normal recovery course.

Statistical Support

Support for statistical analyses will be provided by [name], MSPH, a trained biostatistician, working for the Department of Surgery at Emory University Hospital. All analyses will be conducted or supervised by [name]. [name] has 15 years of experience in data analysis and 7 years of experience working as the department statistician for surgery. He has over 40 peer-reviewed publications to his name and experience with outcomes and health services research as well as basic science research. In the past, he has assisted in the design and analysis of similar trials at Emory University. Regarding the cost-effective analysis, [name] is the primary mentor. He is an experienced researcher and participated in cost-effective research in GMH by comparing the cost effectiveness of 2 types of mandibular fracture treatment. ⁽²⁴⁾

Inclusion & Exclusion Criteria

- The following subjects will be included in the study:
 - 1- Agreed to be enrolled in the study.
 - 2- Indications for surgical repair of orbital floor and/ wall fractures are dependent on several factors:
 - a. Correction or prevention of cosmetic deformity (enophthalmos or inferior dystopia; disruption of greater than 50% of the orbital floor is likely to cause cosmetically apparent enophthalmos.

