Data	Time
Age, sex, race, DOB	Pre-operative (pre-op)
Mechanism of injury, time from injury to admission	Pre-op
Type of orbital fracture and other injuries	Pre-op
Indications for surgery	Pre-op
CT scans results (fracture size & location)	Pre-op
Extra-ocular motility indicating which gaze	Pre-op
Level of infraorbital nerve injury	Pre-op
Traumatic pupillary mydriasis	Pre-op
IOP (Intra-ocular pressure)	Pre-op
Enophthalmos (Hertel exophthalmometer measurement)	Pre-op
The use of 3D printed models	Pre-op
The time needed to print the model	Pre-op
Orbital and ocular exam results	Pre-op
Time from admission to surgery	Pre-op
Date of surgery	Pre-op
Length of surgery (minutes)	Operative
Approach	Operative
Intra-operative complications	Operative
Post-operative orbital volume comparison (OsiriX)	Post-operative
Dates of post-operative visits	Post-operative, weeks 1, 3, and 6
Extra-ocular motility indicating which gaze	Post-operative, weeks 1, 3, and 6
Level of infraorbital nerve injury	Post-operative, weeks 1, 3, and 6
Traumatic pupillary mydriasis	Post-operative, weeks 1, 3, and 6
IOP (Intra-ocular pressure)	Post-operative, weeks 1, 3, and 6
Infection	Post-operative, weeks 1, 3, and 6
Enophthalmos (Hertel exophthalmometer measurement)	Weeks 1, 3, and, 6

Overall cost	Post-operative
Need for second surgical procedure	Post-operative, weeks 1, 3, and 6

SIGNIFICANCE AND INNOVATION

This project will test two new and evolving methodologies in the medical world: 1) an office-based 3D printer and 2) pre-adjusted patient-specific implants. These two methodologies have yet to be applied together in orbital fracture reconstruction. Additionally, this study focuses on low-income patients and will be the first of its kind serving this population. Several other benefits include potential savings related to total overall cost, a reduced operative time and postoperative course, and a subsequent increase in both the quality of care and the value of care, especially in the underserved patient population cared for at GMH. We expect the results of this study to be applicable at most major urban trauma centers across the USA and abroad. The results of this study can be used in future studies as a model or pilot study.

FUTURE PLANS

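### The primary volume comparison does not adjust for pre-operative injury size, although each patient's existing CT can supply it: a cheap gain in efficiency, larger if the outcome is the reduction from post-traumatic volume

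*Combined protocol and SAP*

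**What the plan says.** The Randomization & Statistical Analysis section sets the test for the primary outcome and for operating time: "Two-sample t-tests or Wilcoxon-Mann-Whitney tests (if data are non-parametric) will be used to compare mean orbital volume differences and operative times". It names no covariate. The only multivariable work mentioned there is optional and aims at risk factors for complications or an abnormal recovery. Randomization is stratified by surgeon/specialty only, so injury size is not controlled by design either.

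The sample size section rests on the same kind of test, a "t-test to compare the difference in contralateral orbital volume between the treatment and control groups". It takes a "sample size of 60", "evenly split between the new treatment and control groups", to "detect at least a 1 cm³ difference in orbital volume" with an "alpha level of .05, and 1.17 cm³ standard deviation of orbital volume".

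Under Study Settings and Patients, the primary outcome is introduced as the injured orbit's volume compared with the contralateral orbit. It is then classified under item A as "The absolute reduction in orbital volume from the measured post-traumatic volume, as measured by CT".

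Preoperative Assessment requires a maxillofacial CT for all patients. The Data Collection & Analysis table lists "CT scans results (fracture size & location") and the type of orbital fracture as pre-operative items. Its only orbital volume row is post-operative.

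**The concern.** Patients will differ in how much orbital volume the injury added. The protocol distinguishes isolated one-wall fractures from complex ones, and its Length of stay and Intra-operative Assessment text provides for both. The BACKGROUND counts at the site (90 isolated of 126) leave 36/126, about 29%, complex. If injury size predicts how close the repaired orbit comes to its partner, or how long the repair takes, a plain two-sample test leaves that variation in the error term.

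The matter is sharper under item A. A good repair of a large defect gives a large reduction and a good repair of a small defect gives a small one, whichever implant is used. An unadjusted comparison of reductions therefore carries the spread of injury size as noise.

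**Working it through.** **Inputs from the documents.** 30 per arm, difference 1 cm³, SD 1.17 cm³, alpha 0.05. Sidedness is not stated; two-sided reproduces the plan's figures. The stated shortfall of 25% leaves 60 × 0.75 = 45 patients, or 22.5 per arm.

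**Inputs assumed.** r is the within-arm correlation between the pre-operative and post-operative injured-minus-uninjured differences, taken from 0 to 0.6. SDpre is the SD of the pre-operative difference, taken as 1, 2 or 3 cm³. Neither is in the documents.

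**Step 1, the plan's own figures.** Two-sided t-test, noncentral t, noncentrality = 1 / (1.17 × √(2/n)), 2n − 2 degrees of freedom. Power is 90.2% at n = 30 and 80.0% at n = 22.5. The stated 90% and 80% reproduce.

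**Step 2, adjustment on the powered outcome.** With baseline in the model (ANCOVA) the residual SD is 1.17 × √(1 − r²), with one degree of freedom fewer.

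| r | residual SD (cm³) | power, 60 patients | power, 45 patients |
|---|---|---|---|
| unadjusted | 1.170 | 90.2% | 80.0% |
| 0.1 | 1.164 | 90.5% | 80.4% |
| 0.2 | 1.146 | 91.3% | 81.6% |
| 0.3 | 1.116 | 92.7% | 83.5% |
| 0.45 | 1.045 | 95.4% | 88.0% |
| 0.6 | 0.936 | 98.2% | 93.8% |

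If the covariate is useless (r = 0), power with 60 patients is 90.22% adjusted against 90.23% unadjusted. The price of adjusting is negligible.

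**Step 3, item A tested unadjusted.** The SD of the reduction is √(1.17² + SDpre² − 2 × r × 1.17 × SDpre). For SDpre = 2 and r = 0 this is √(1.369 + 4) = 2.32 cm³. Power with 30 per arm:

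| SDpre (cm³) | r = 0 | r = 0.3 | r = 0.6 |
|---|---|---|---|
| 1 | 70% | 84% | 97% |
| 2 | 38% | 48% | 66% |
| 3 | 22% | 26% | 34% |
| ANCOVA, any SDpre | 90% | 93% | 98% |

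**Step 4, why the last row serves both outcomes.** If the uninjured orbit's volume is taken as the same before and after surgery, the reduction equals the pre-operative difference minus the post-operative difference. Once the pre-operative difference is in the model, modelling the reduction or the post-operative difference gives the same treatment effect with the sign reversed, and the same residual SD.

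**The case against.** The strongest reply is that the plan is sound as it stands. Under randomization an unadjusted two-sample test is valid. On the contralateral difference, which is what the sample size section powers and what the words of the analysis section most naturally describe, it delivers the stated 90%. The gain from adjusting depends on a correlation that nobody has documented. The abstract reports a relation between post-traumatic volume and enophthalmos, not residual volume after repair. Surgery aims to remove the excess, and the residual error can go either way, so r of 0.1 or 0.2 is plausible and the gain would then be 0.3 or 1.1 percentage points. The fracture mix is also uncertain, since the inclusion criteria call for a unilateral orbital floor fracture. All of this stands, and it limits the point to efficiency.

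Three stronger readings are tempting, and the documents do not support them:

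- That the plan ignores post-traumatic volume. Item A subtracts it. Subtraction is not adjustment, but it is not neglect either.
- That the low powers in Step 3 measure the cost of leaving a covariate out of the planned test. They do not. At r = 0, ANCOVA does no better than the plain t-test on the contralateral difference (both 90.2%). Those losses come from testing an unadjusted reduction, and they shrink as r rises.
- That the trial is underpowered. On the plan's own assumptions it is not.

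The objection does not remove the case for adjusting. The data exist, the cost at r = 0 is about 0.01 percentage points of power, and the plan leaves open which of the two outcomes will be tested.

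**Conclusion.** A cheap improvement, not an error. The planned primary test makes no use of pre-operative injury size as a covariate, although the existing CT can supply it.

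On the contralateral difference, adjustment lifts power from 90.2% to between 90.5% and 98.2% for assumed correlations of 0.1 to 0.6, and from 80.0% to between 80.4% and 93.8% if only 45 patients are enrolled. The lower end of the range is small and cannot be excluded. If item A is what gets tested, unadjusted power lies anywhere from 22% to 97% over the assumed grid, and adjustment brings it to about 90% to 98%.

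All figures take the plan's 1.17 cm³ as the SD of the post-operative difference. The sample size section describes it as an SD of orbital volume, so the 90% has no demonstrated margin. If that SD were 1.5 cm³ (an assumption), unadjusted power would be 71.9%, against 75.8% with adjustment at r = 0.3. No power figure can be given for operating time, because the documents state neither an effect size nor an SD for it.

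**What to change.** 1. Prespecify the primary analysis as a linear model of the signed post-operative injured-minus-uninjured volume difference on arm, the pre-operative injured-minus-uninjured volume difference, and fracture type (isolated or complex). Naming the modelled outcome is essential, because Step 3 shows that the choice matters more than the covariate.
2. Add a pre-operative orbital volume row (both orbits) to the Data Collection & Analysis table, measured in both arms from the existing CT with the same software as the post-operative volume.
3. Keep the t-test or Wilcoxon test as a sensitivity analysis.
4. Adjust the comparison of operating time for fracture type and size, which are already collected.

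The cost is a change of wording, one software measurement per existing CT, and one or two degrees of freedom. No extra scan or patient is needed.

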Traditional methods of orbital fractures reconstruction involve intra-operative shaping of orbital implants (titanium mesh). ⁽¹⁰⁾ Orbital fracture reconstruction using selective laser-melting patient-specific implants has been found to be superior to traditional reconstruction methods. ^(8, 11, 12) The challenges with the traditional approach are a significant increase in cost and longer preoperative time (production time). ^(11, 12) There have been no comparisons published between the traditional approach and pre-adjusted patient-specific orbital implants with respect to orbital volume reconstruction.

- Hypothesis #1: Pre-adjusted patient-specific orbital implants will **more accurately restore the orbital volume** to pre-trauma measures than non-patient-specific orbital implants.

Aim #2: To compare postoperative complications.

The main complications due to orbital fractures reconstruction are 1) enophthalmos and 2) diplopia as a result of inadequate orbital volume reconstruction. The incidence of enophthalmos after the traditional orbital reconstruction approach is 7–27%. ^(5, 13, 14) This rate is significantly higher than that observed after using the patient-specific approach (3.7%). ⁽¹²⁾ Again, there are currently no data regarding pre-adjusted, patient-specific orbital floor implants. The incidence of

diplopia after the traditional orbital reconstruction approach is 8–42%,^(14–16) which is significantly higher than that for the patient-specific approach (3.2%).⁽¹²⁾

- **Hypothesis #2:** Pre-adjusted patient-specific orbital implants will **have fewer postoperative complications** than non-patient-specific orbital implants.

Aim #3: To evaluate the length of hospital stay. The typical hospital stay for an orbital floor fracture at Grady Memorial Hospital (GMH) is 1–2 days, depending on the patient's response to surgery.

- **Hypothesis #3:** Pre-adjusted patient-specific orbital implants lead to a **shorter length of stay**, secondary to improved accuracy of implant design, placement, and reduced need for manipulation. This would be expected to lead to decreased postoperative swelling and pain. Orbital fracture reconstruction could be executed as a same-day surgery (outpatient surgery) when utilizing 3DP.

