- Complex orbital fractures will be exposed and identified via a transconjunctival approach in combination with lateral cantholysis if needed to improve access.
- To record and compare the operative time between the two groups, a stopwatch will be utilized. The time in minutes will be recorded from fracture exposure and identification to final implant placement and fixation.

Postoperative Assessment

During post-operative care, all patients will undergo the following:

- 1) Maxillofacial non-contrast CT scans according to the protocol will be obtained as part of the standard of care in managing orbital fractures.
- 2) The PI will evaluate the orbital volume using OsiriX (medical software). Orbital volume measurements will be obtained to compare the injured and uninjured (contralateral) orbital volumes. OsiriX MD offers advanced processing techniques and has the ability to precisely measure orbital volume. It utilizes the DICOM data from the immediate post-operative CT scans.
- 3) All patients, regardless of the group into which they are randomized, will receive their post-operative assessment by the designated team resident under the supervision of one of the following attendings: [name] for OMFS, [name] for ENT, or [name] for Plastic Surgery.
- 4) All patients, regardless of the group into which they are randomized, will receive their post-operative ocular assessment by [name], ophthalmology attending and Co-PI, or by her fellow [name].

Follow-Up

- All patients will be regularly assessed at 1 week, 3 weeks, and 6 weeks postoperatively.

This is a standard post-operative follow-up schedule for craniomaxillofacial fracture patients. It is also an adequate duration for edema to resolve, which will assist in the accurate evaluation of enophthalmos. The following will be evaluated and recorded by the surgical team at each follow-up visit: enophthalmos, infection, infraorbital nerve injury, traumatic pupillary mydriasis, orbital compartment syndrome, and restricted extra-ocular movement.

- In terms of data collection and data extraction from Epic: PI [name], co-PI [name] and an assigned research coordinator will be involved.

Patient Compensation

All patients enrolled in the study will be compensated with \$100 for their time and to encourage compliance. Their compensation includes the costs of participation in the study (\$50) and the completion of the follow-up visits at week 6.

Data Collection & Analysis

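### Hypothesis 1 is about accuracy of orbital volume restoration, but neither definition of the primary variable is an unsigned distance from the normal orbit

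*Combined protocol and SAP*

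**What the plan says.** The study question in the Abstract and Hypothesis #1 under Specific Aims both concern accuracy: the pre-adjusted implants are expected to "more accurately restore the orbital volume" compared with standard implants.

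The primary variable is described in two ways under Study Settings and Patients. The first is a comparison with the other side: "The primary outcome variable is the orbital volume of the injured orbit compared to the contralateral uninjured orbit as assessed by CT scan". The second follows directly as item A: "The absolute reduction in orbital volume from the measured post-traumatic volume, as measured by CT".

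The later sections mainly follow the first description. The sample size rests on a two-sample t-test "to compare the difference in contralateral orbital volume between the treatment and control groups", powered to "detect at least a 1 cm³ difference in orbital volume" with an SD of 1.17 cm³. Postoperative Assessment states that "Orbital volume measurements will be obtained to compare the injured and uninjured (contralateral) orbital volumes". Under Randomization & Statistical Analysis, two-sample t-tests or Wilcoxon-Mann-Whitney tests "will be used to compare mean orbital volume differences and operative times".

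No section takes the absolute value, the square or any other unsigned distance of the injured-minus-contralateral difference, and none states a sign convention. For volume, the word absolute appears only in item A, where it describes a reduction from the injured baseline. The secondary 2 cm³ criteria are not written as unsigned distances either.

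**The concern.** Accuracy is how far a repaired orbit lies from its normal volume, whichever side it falls on. A mean of differences is signed unless the plan says otherwise. One patient at +2 cm³ and another at -2 cm³ then average to zero, exactly as two perfect repairs would. The Wilcoxon alternative compares location and has the same property.

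Item A does not solve this. It rewards a larger reduction without limit, so it cannot separate an exact repair from an over-correction.

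Two wrong conclusions become possible on the primary hypothesis: a real gain in accuracy goes unseen, or a shift in average direction is reported as a gain. The silence also leaves the choice between signed and unsigned analysis open until data exist. This matters in a trial where surgeon and patient are unblinded and the PI measures the volumes, with no statement that this reading is blinded.

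**Working it through.** **1. The plan's own figure.** Inputs from Randomization Sample Size & Calculation: difference 1 cm³, SD 1.17 cm³, alpha 0.05 (two-sided assumed; sidedness is not stated), power 90%. Standardised effect = 1/1.17 = 0.855. The noncentral-t calculation gives 29.76, so 30 per arm and 60 in total; power at 30 per arm is 90.2%. A 25% shortfall leaves 45 patients (22 and 23), with power 80.0%. Both stated figures reproduce, for a shift in a mean.

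**2. The two definitions.** Let D = post-operative injured volume minus contralateral volume. D > 0 is under-correction and D < 0 over-correction. Item A is then

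reduction = (post-traumatic volume - contralateral volume) - D.

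It falls as D rises and has no optimum at D = 0. Illustration (assumed): if the injured orbit starts 3 cm³ too large, an exact repair scores 3 - 0 = 3 and an over-correction by 1 cm³ scores 3 - (-1) = 4. Under randomisation the first term has the same expectation in both arms, so a comparison of mean reductions is again a comparison of signed mean D, with added variance from injury size.

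**3. What each test detects.** The document gives no mean or SD of D by arm, so all scenarios are assumptions. The 1.17 cm³ is the plan's figure, but it is given as an SD of orbital volume, not of D or |D|. For normal D with mean m and SD s,

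mean |D| = s·√(2/π)·exp(-m²/(2s²)) + m·[1 - 2Φ(-m/s)].

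Example: m = 0, s = 1.17 gives 1.17 × 0.798 = 0.93; s = 0.585 gives 0.47.

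Simulation with 40,000 trials per row, 30 per arm, two-sided 0.05. Signed = pooled t-test on D; unsigned = Welch t-test on |D|. Entries are the percentage of trials significant.

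| Control mean (SD) | Group A mean (SD) | Mean \|D\|, control vs A | Signed | Unsigned |
|---|---|---|---|---|
| 0 (1.17) | 0 (0.585) | 0.93 vs 0.47 | 5% | 92% |
| +0.5 (1.17) | -0.5 (1.17) | 1.02 vs 1.02 | 90% | 5% |
| 0 (1.17) | -1 (1.17) | 0.93 vs 1.25 | 90% | 33%, all against A |
| +1 (1.17) | 0 (1.17) | 1.25 vs 0.93 | 90% | 33% |
| +1.5 (1.17) | +0.5 (1.17) | 1.61 vs 1.02 | 90% | 71% |
| +2 (1.17) | +1 (1.17) | 2.04 vs 1.25 | 90% | 85% |
| +3 (1.17) | +2 (1.17) | 3.00 vs 2.04 | 90% | 90% |
| +1 (1.17) | +0.25 (0.585) | 1.25 vs 0.51 | 87% | 99% |

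The Wilcoxon test on signed D behaves like the signed t-test: about 5% to 6% in the first row and 88% to 89% in the second.

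**4. Reading the table.** Row 1 is an accuracy gain that the signed test cannot see. Row 2 is a significant result with equal accuracy, and in row 3 Group A is less accurate. Rows 4 to 7 keep the plan's 1 cm³ shift and move it away from zero. Over-corrections are a fraction Φ(-m/s) of each arm: in row 7, Φ(-3/1.17) = 0.5% and Φ(-2/1.17) = 4.4%, so almost nothing cancels and the tests agree.

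**The case against.** The strongest reply is that the plan is silent rather than explicitly signed. Its word for the contrast is undefined, and for enophthalmos the same section uses a difference between orbits as a size. A reader might infer that the sponsor chose a signed analysis; the document does not show that. What stands is that the plan, followed as written, defaults to signed means, and nothing in it directs the analyst otherwise.

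Second, the volume-related harm that the plan describes is mainly one-directional. Background and Aim #2 link enophthalmos and diplopia to insufficient restoration, over-correction is not named, and the sample size assumes a mean shift. If repairs err almost always towards under-correction, the signed test works. This is a fair limit, but no data on the direction of residual errors are given. That pre-bending to a mirrored model mainly reduces scatter is plausible, yet it is an assumption of this review and not a statement in the plan.

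Third, when the arm means lie on opposite sides of zero, reporting them would expose a misleading result, and the 2 cm³ classification, enophthalmos and plate contour give separate evidence. These soften the harm; they do not make the primary test one of accuracy.

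Fourth, an unsigned endpoint can cost a lot of power. That stands in full and is carried into the fix.

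**Conclusion.** The point holds: neither stated form of the primary variable measures the accuracy that Hypothesis 1 claims, and the two forms also conflict with each other. It goes beyond missing detail, because carrying out the plan as written can lead to a wrong conclusion on the primary question.

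The size depends on where errors fall. With errors on both sides of zero, the signed test can have 5% power against a halving of error, or be significant in 90% of trials with no accuracy difference. With nearly all errors on one side, the choice makes no practical difference. Every scenario assumes normal D, and all arm means, as well as the halved SD, are assumptions.

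Two stronger readings are not supported. One is that the trial has only 5% power: that figure needs both arms centred on zero. The other is that 60 patients was miscalculated: the number is right for a 1 cm³ mean shift, but it does not carry over automatically to an unsigned deviation.

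**What to change.** - Reconcile the two definitions into one primary variable per patient: the absolute value of (injured minus contralateral orbital volume, cm³) on the immediate post-operative CT. Use it in the outcome, sample size and analysis sections alike.
- Name the test in advance, Welch t-test or Wilcoxon. |D| is skewed.
- Report by arm, as supporting results, the signed difference with its sign convention and the reduction from the post-traumatic volume.
- Base the conclusion on accuracy on the absolute deviation only.

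The same CT volumes serve, so no new data, visits or procedures are needed. The cost is in power. The stated 90% must be restated for |D| at the planned 60 patients, with an SD for |D| in place of the SD of orbital volume. For the same 1 cm³ shift the range is about 33% (+1 vs 0), 71% (+1.5 vs +0.5), 85% (+2 vs +1) and 90% (+3 vs +2); it is higher if scatter also falls (99% in the last row of the table).

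To hold 90% in the two weakest cases, the normal approximation n = (1.96 + 1.2816)² × (SD₁² + SD₂²)/(difference in mean |D|)² gives 10.51 × (0.891² + 0.705²)/0.321², about 131 per arm at +1 vs 0, and 10.51 × (1.012² + 0.764²)/0.594², about 48 per arm at +1.5 vs +0.5, against the planned 30. The sponsor should state which case it considers realistic and why.
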